## 4. SELECTION AND ENROLLMENT OF PARTICIPANTS

### 4.1 Inclusion Criteria

Subjects must meet all of the following inclusion criteria to be eligible for enrollment in the study:

- Diagnosed COVID+ status by physician. Either became symptomatic in the prior 10 days, or if not symptomatic, likely infected/exposed within the prior 10 days.
- Individuals (all sex, all gender) at least 18 years of age and at most 65 years of age and in good oral health without any known allergies to commercial dental products or cosmetics.
- Evidence of a personally signed and dated informed consent document indicating the subject (or legally acceptable representative) has been informed of all pertinent aspects of the trial and all of their questions have been answered.
- Able to comprehend and follow the requirements of the study (including availability on scheduled visit dates) based on research site personnel's assessment.
- Females of childbearing potential will have a negative urine pregnancy test (on site) or be physically incapable of pregnancy (implants or injections, Intrauterine device, Bilateral tubal ligation, Hysterectomy, Ovariectomy, Women post-menopausal)

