### 4.2 Exclusion Criteria

Subjects presenting with any of the following will not be included in the study:

- Patients who have been eating or drinking within an hour of the study
- Patients under 18 years old and older than 65 years old
- Subjects presenting with and/or self-reporting any of the following will not be included in the study:
  - history of significant adverse effects following use of oral hygiene products such as toothpastes and mouthrinses. (self-reported)
  - Self-reported allergy to iodine, ethanol, essential oils (Eucalyptol, Menthol, Methyl salicylate, Thymol), hydrogen peroxide, chlorhexidine gluconate, peroxy, listerine, betadine, peridex, cetylpyridinium chloride, and other components in the mouth rinses (methyl salicylate, ethanol, saccharin sodium, glycerin, propylene glycol, sorbitol, *FD&C blue no. 1*, Poloxamer 407, Benzoic acid, Zinc chloride, Sodium benzoate, Sucralose, PEG-40 sorbitan diisostearate, potassium sorbate, citric acid).
  - History of serious medical conditions that, at the discretion of the Investigator, will disqualify the subject. (Self-reported)

- A history of severe dry mouth (xerostomia), drug-induced xerostomia (antidepressants, anticonvulsants, antihypertensives), or Sjogren’s syndrome
- A history of recent (within the last 30 days) or current **recent oral herpes flare up**, candida (thrush) infection, aphthous ulcer flare up, current/active severe periodontal disease, or other recent oral viral infection or flare up within the past 30 days (self-reported)
- Current history of alcohol or drug abuse (self-reported).
- History of drinking water or eating food within an hour of the study visit.
- History of drinking alcohol within 12 hours of the study visit.
- History of using a commercial mouthrinse within 24 hours of the study visit.
- Participation in any study involving oral care products, concurrently or within the previous 30 days. (self-reported)
- Positive pregnancy test, reported pregnancy or lactation (this criterion is due to oral tissue changes related to pregnancy and nursing which can affect interpretation of study results. Additionally, women are advised to check with their physician before using Povidone-iodine during pregnancy and lactation, which cannot occur in a blinded, randomized trial.)

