  - Iodine freely crosses the placenta and is secreted in breast milk. Thyroid function disorders have been reported in the offspring of mothers exposed to pharmacological doses of iodine. Povidone iodine should not be used regularly during pregnancy unless there is no alternative treatment available.
- Do not use Betadine Gargle and Mouthwash 10mg/ml Oral Solution: - if you are allergic (hypersensitive) to povidone iodine or any of the other ingredients listed - if you currently have or have ever had a thyroid problem, including swelling (nodular colloid goitre, endemic goitre or Hashimoto's thyroiditis), as using Betadine Gargle and Mouthwash in these circumstances can further affect the function of your thyroid - if you are currently having lithium therapy for depression as this type of medicine can interact with Betadine Gargle and Mouthwash to affect the function of your thyroid - on children of 6 years and under. Talk to your doctor or pharmacist before using Betadine Gargle and Mouthwash 10mg/ml Oral Solution - if your skin is broken (for example, due to a burn) as using Betadine Gargle and Mouthwash in these circumstances may cause toxic levels of iodine to be absorbed into your blood - if you currently have or have ever had a kidney problem as using Betadine Gargle and Mouthwash in these circumstances may cause toxic levels of iodine to be absorbed into your blood - when you know you are due to have a thyroid, faeces (stool) or urine test as Betadine Gargle and Mouthwash may affect the results.

1.5% w/v hydrogen peroxide rinse
	
 
● Pregnancy and lactation 
 
○ Although there is not sufficient specific clinical data on the use of 1.5
 
○ % w/v hydrogen peroxide rinse in this patient group, self-administration without medical advice is not recommended.
 
 
 
● Do not use in children under 12
 

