
Females of childbearing potential will have a negative urine pregnancy test (on site) or be physically incapable of pregnancy (implants or injections, Intrauterine device, Bilateral tubal ligation, Hysterectomy, Ovariectomy, Women post-menopausal)
	
Positive pregnancy test, reported pregnancy or lactation.

	A history of recent (within the last 30 days) or current recent oral herpes flare up, candida (thrush) infection, apthous ulcer flare up, current/active severe periodontal disease with bleeding gums, or other recent oral viral infection or flare up within the past 30 days.
--	---

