### 4.3 Study Enrollment Procedures

Outpatient subjects will be recruited from patients seen in the UNC Respiratory Distress Clinic (RDC) and other UNC testing facilities who have tested positive for COVID+ and consented to be contacted for participation in COVID-related research studies. The subjects are being approached by phone or email have signed a prior facility consent at the Respiratory Distress Clinic confirming their willingness to share their name and contact information to be contacted for study participation in COVID related research. We will not receive information on subjects that decline this internal consent. Subjects will be contacted for recruitment by phone and (if unreachable by phone) by secure email by study personnel; patients will have the study rationale and risks explained and will be provided time to ask questions and consider participation. If patients are interested in participating, a single appointment will be scheduled for them at the Adams School of Dentistry Go Health Clinical research core. Consent documentation will be signed in person and in private in the Go Health Clinical Research Core. For Spanish speaking patients and/or parents, Spanish forms will be provided and communication will occur through a Spanish translator. All patients are adults and over normal cognitive capacity, and therefore will be able to consent for themselves. A list of COVID+ subjects that have consented to be contacted for research, will be provided by the RDC clinic, sent via secure UNC servers or secure UNC email to our research team's clinical coordinator, and this list will include names and contact details (PHI). This list is updated daily and provided to approved research sites, including ours.

At the visit, a consented patient will answer screening questions regarding inclusion and exclusion criteria. Answers will be entered into the CDART research database managed by UNC. Prior to finalizing these screening questions, women participants of childbearing potential will be asked to provide a urine sample in the restroom, to undergo a rapid pregnancy test by study personnel. Any pregnant or lactating patients will be excluded.

Our study statistician, [name], will create a block randomization schedule and perform these computations. All patients will be consented and then fill out our screening questions for inclusion and exclusion to confirm eligibility prior to being assigned to the randomization schedule.

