#### **5.3.2 Required Interventions**

The patient will rinse with a blinded mouthrinse for 60 seconds and then will spit it out, followed by donating saliva samples.

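### Users of contraceptive implants, injections and intrauterine devices are wrongly counted as physically unable to become pregnant, so they can qualify without the on-site urine test

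*Combined protocol and SAP*

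**What the plan says.** Section 4.1 gives a woman two ways to satisfy the pregnancy criterion: "Females of childbearing potential will have a negative urine pregnancy test (on site) or be physically incapable of pregnancy (implants or injections, Intrauterine device". The rest of the bracket names tubal ligation, hysterectomy, ovariectomy and menopause. The summary table of inclusion and exclusion criteria repeats the second route in full: "or be physically incapable of pregnancy (implants or injections, Intrauterine device, Bilateral tubal ligation, Hysterectomy, Ovariectomy, Women post-menopausal".

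The procedure is described in section 4.3: "women participants of childbearing potential will be asked to provide a urine sample in the restroom, to undergo a rapid pregnancy test by study personnel". Sections 6.2.1 and 11.2 repeat it. None of the three says who counts as being of childbearing potential, and no other section does. The schedule in section 6.1 marks a urine pregnancy test at the single visit without saying who takes it.

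The matching exclusion in section 4.2 is "Positive pregnancy test, reported pregnancy or lactation". It gives two reasons. Oral tissue changes in pregnancy and nursing may disturb interpretation of the results. Also, women are advised to ask a physician before using povidone-iodine, which a blinded randomised trial does not allow.

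**The concern.** Contraception lowers the chance of pregnancy but does not make it physically impossible. Putting three reversible methods in the same list as hysterectomy is therefore a factual error, and the 'or' turns the error into a way round the test.

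What is at stake is the detection of a pregnancy the woman does not know about. That is the case an on-site test exists to find, since a known pregnancy would be reported anyway. The participant can neither know nor choose her rinse, so screening is the only safeguard. The arm-specific table in section 4.2 carries pregnancy cautions for three of the five active rinses: povidone-iodine, hydrogen peroxide and chlorhexidine. The oral-tissue reason applies in every arm.

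**Working it through.** The plan states no figure on this point and none has to be recomputed. The check is a count of the list and a comparison of the sections.

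1. **Count the list.** Section 4.1 and the summary table name the same conditions. Taking implants and injections separately, they are implants, injections, intrauterine device, bilateral tubal ligation, hysterectomy, ovariectomy and post-menopausal status, which makes 7. Reversible contraception accounts for 3 of them (implants, injections, intrauterine device). The remainder is 7 − 3 = 4.

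2. **Read the criterion literally.** It has the form: negative test, or on the list. A woman with an intrauterine device is on the list, so she meets the criterion with no test result. The sentence also contradicts itself, because its subject is women of childbearing potential and its second branch describes them as unable to conceive.

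3. **See whether the procedural text closes the gap.** There are two readings.
   - *The list describes a subset of women of childbearing potential.* Sections 4.3, 6.2.1 and 11.2 would then test contraceptive users, although section 4.1 would not require the result for eligibility.
   - *The list says who falls outside childbearing potential.* Those sections then do not reach contraceptive users, and they go untested.

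   With the term undefined, the list in section 4.1 is the only text that bears on its meaning. Two staff members could treat the same woman differently and both cite the protocol. The schedule in section 6.1 does not decide between the readings.

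4. **See whether the exclusion closes the gap.** Section 4.2 acts on a positive test or on a reported pregnancy or lactation. A woman who is untested and unaware of a pregnancy triggers none of these. The statement in sections 4.3, 6.2.1 and 11.2 that pregnant or lactating patients are excluded is broader, but it cannot act on a pregnancy nobody has detected.

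5. **Size in participants.** The documents give no contraceptive use, no pregnancy prevalence and no expected number of women among the 480 planned participants. No count can be derived.

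**The case against.** The strongest reply is that the wrong label is certain but the missed test is not. On the first reading in step 3, contraceptive users are tested, and both the schedule and the broad exclusion of pregnant patients lean that way. This stands as far as it goes: the text leaves the matter open and does not establish that these women go untested. It does not rescue the criterion, which should not depend on which reading staff adopt.

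A second reply is that a sponsor could reasonably accept long-acting contraception in place of a test when the exposure is this slight: "The patient will rinse with a blinded mouthrinse for 60 seconds and then will spit it out". The povidone-iodine label text likewise concerns repeated use: "Povidone iodine should not be used regularly during pregnancy unless there is no alternative treatment available". These points keep the matter minor. If that policy was intended, however, the protocol should state it as a policy. What it states is that these women cannot become pregnant, which is untrue.

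Third, 3 of 7 counts list entries and not participants, and it splits one printed entry (implants or injections) into two. That is correct. The fraction describes the wording error only.

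Fourth, the four remaining conditions are not watertight. Ovariectomy is not said to be bilateral, and menopause is undefined. This is a fair refinement and is easily added to the same edit. It does not count against removing the three contraceptive methods.

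**Conclusion.** The point holds and is minor. Three of the seven conditions offered as physical incapacity for pregnancy are reversible contraception. Read literally, their users qualify untested, and no other section settles that they are tested. An unrecognised pregnancy in such a woman could be missed.

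The expectation that few women are affected is a judgement, because the documents contain no figure to support or contradict it. The consequence for any one participant is limited, since exposure is a single rinse and a reported pregnancy still excludes her. Sample size, power, type I error and the planned analyses do not depend on this criterion.

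The conclusion assumes that implants and injections here mean contraceptive ones, the only sensible meaning in this list.

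**What to change.** Remove implants, injections and intrauterine devices from the list in section 4.1 and from the summary table. In section 4.1, define childbearing potential once, as applying to every woman who is not surgically sterile (bilateral tubal ligation, hysterectomy, ovariectomy) or post-menopausal, and require a negative on-site urine test from all such women. Sections 4.3, 6.2.1 and 11.2 already use the term and already confirm eligibility before randomisation or participation, so they need no change. While editing, it would help to specify bilateral ovariectomy and to say how post-menopausal status is established.

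The cost is two wording edits, one of which carries the definition, and a few more rapid urine tests of the kind already done at the visit.

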### 4.2 Exclusion Criteria

Subjects presenting with any of the following will not be included in the study:

- Patients who have been eating or drinking within an hour of the study
- Patients under 18 years old and older than 65 years old
- Subjects presenting with and/or self-reporting any of the following will not be included in the study:
  - history of significant adverse effects following use of oral hygiene products such as toothpastes and mouthrinses. (self-reported)
  - Self-reported allergy to iodine, ethanol, essential oils (Eucalyptol, Menthol, Methyl salicylate, Thymol), hydrogen peroxide, chlorhexidine gluconate, peroxy, listerine, betadine, peridex, cetylpyridinium chloride, and other components in the mouth rinses (methyl salicylate, ethanol, saccharin sodium, glycerin, propylene glycol, sorbitol, *FD&C blue no. 1*, Poloxamer 407, Benzoic acid, Zinc chloride, Sodium benzoate, Sucralose, PEG-40 sorbitan diisostearate, potassium sorbate, citric acid).
  - History of serious medical conditions that, at the discretion of the Investigator, will disqualify the subject. (Self-reported)

- A history of severe dry mouth (xerostomia), drug-induced xerostomia (antidepressants, anticonvulsants, antihypertensives), or Sjogren’s syndrome
- A history of recent (within the last 30 days) or current **recent oral herpes flare up**, candida (thrush) infection, aphthous ulcer flare up, current/active severe periodontal disease, or other recent oral viral infection or flare up within the past 30 days (self-reported)
- Current history of alcohol or drug abuse (self-reported).
- History of drinking water or eating food within an hour of the study visit.
- History of drinking alcohol within 12 hours of the study visit.
- History of using a commercial mouthrinse within 24 hours of the study visit.
- Participation in any study involving oral care products, concurrently or within the previous 30 days. (self-reported)
- Positive pregnancy test, reported pregnancy or lactation (this criterion is due to oral tissue changes related to pregnancy and nursing which can affect interpretation of study results. Additionally, women are advised to check with their physician before using Povidone-iodine during pregnancy and lactation, which cannot occur in a blinded, randomized trial.)
- Other severe acute or chronic medical or psychiatric condition or laboratory abnormality that may increase the risk associated with trial participation or investigational product administration or may interfere with the interpretation of trial results and, in the judgment of the Investigator, would make the subject inappropriate for entry into this trial.
- Patient with developmental/cognitive disability that cannot self-consent, comprehend and follow the requirements of the study based on research site personnel’s assessment.
- Patient who has or ever had a thyroid problem, including swelling (nodular colloid goitre, endemic goitre or Hashimoto’s thyroiditis)
- Patients currently having lithium therapy for depression
- Patients with sizable mucosal tears, abrasions, growths or burns in the mouth
- Patients with kidney dysfunction
- The following table lists exclusion criteria specific to each mouth rinse proposed in the study:

mouthrinse*	Exclusions
26.9% ethanol plus essential oils	
 
● Do not use in children under 12
 

1% w/v povidone-iodide (PVI)

- Hypersensitivity to iodine, polyvinyl pyrrolidone or to any excipient.
- History of abnormal thyroid function or goitre (in particular nodular colloid goitre, endemic goitre and Hashimoto's thyroiditis).
  - Use of this preparation may interfere with tests of thyroid function. Iodine is absorbed through burns and broken skin and to a lesser extent through intact skin and may lead to toxic levels of iodine in the blood, particularly in patients with renal insufficiency. If symptoms occur suggesting changes in thyroid function, these should be investigated. In patients with impaired renal function, blood levels of iodine should be monitored
- Regular use should be avoided in patients on concurrent lithium therapy.
  - Use with concurrent lithium therapy has been shown to exhibit additive hypothyroidic effects. Absorption of iodine from povidone iodine through either intact skin or broken skin may interfere with thyroid function tests. Contamination with povidone iodine of several types of tests for the detection of occult blood in faeces or blood in urine may produce false-positive results.
- Do not use in children of 6 years and under.
- Pregnant or nursing mothers
  - Iodine freely crosses the placenta and is secreted in breast milk. Thyroid function disorders have been reported in the offspring of mothers exposed to pharmacological doses of iodine. Povidone iodine should not be used regularly during pregnancy unless there is no alternative treatment available.
- Do not use Betadine Gargle and Mouthwash 10mg/ml Oral Solution: - if you are allergic (hypersensitive) to povidone iodine or any of the other ingredients listed - if you currently have or have ever had a thyroid problem, including swelling (nodular colloid goitre, endemic goitre or Hashimoto's thyroiditis), as using Betadine Gargle and Mouthwash in these circumstances can further affect the function of your thyroid - if you are currently having lithium therapy for depression as this type of medicine can interact with Betadine Gargle and Mouthwash to affect the function of your thyroid - on children of 6 years and under. Talk to your doctor or pharmacist before using Betadine Gargle and Mouthwash 10mg/ml Oral Solution - if your skin is broken (for example, due to a burn) as using Betadine Gargle and Mouthwash in these circumstances may cause toxic levels of iodine to be absorbed into your blood - if you currently have or have ever had a kidney problem as using Betadine Gargle and Mouthwash in these circumstances may cause toxic levels of iodine to be absorbed into your blood - when you know you are due to have a thyroid, faeces (stool) or urine test as Betadine Gargle and Mouthwash may affect the results.

1.5% w/v hydrogen peroxide rinse
	
 
● Pregnancy and lactation 
 
○ Although there is not sufficient specific clinical data on the use of 1.5
 
○ % w/v hydrogen peroxide rinse in this patient group, self-administration without medical advice is not recommended.
 
 
 
● Do not use in children under 12
 


0.12% Chlorhexidine Gluconate
	
 
● Carcinogenesis, Mutagenesis, Impairment of Fertility 
 
○ In a drinking water study in rats, carcinogenic effects were not observed at doses up to 38 mg/kg/day. Mutagenic effects were not observed in two mammalian in vivo mutagenesis studies with chlorhexidine gluconate. The highest doses of chlorhexidine used in a mouse dominant-lethal assay and a hamster cytogenetics test were 1000 mg/kg/day and 250 mg/kg/day, respectively. No evidence of impaired fertility was observed in rats at doses up to 100 mg/kg/day.
 
 
 
● Pregnancy: Teratogenic Effects 
 
○ Reproduction studies have been performed in rats and rabbits at chlorhexidine gluconate doses up to 300 mg/kg/day and 40 mg/kg/day, respectively, and have not revealed evidence of harm to the fetus. However, adequate and well-controlled studies in pregnant women have not been done. Because animal reproduction studies are not always predictive of human response, this drug should be used during pregnancy only if clearly needed.
 
 
 
● Nursing Mothers 
 
○ It is not known whether this drug is excreted in human milk. Because many drugs are excreted in human milk, caution should be exercised when 0.12% Chlorhexidine Gluconate is administered to a nursing woman. In parturition and lactation studies with rats, no evidence of impaired parturition or of toxic effects to suckling pups was observed when chlorhexidine gluconate was administered to dams at doses up to 100 mg/kg/day.
 
 
 
● Pediatric Use 
 
○ Clinical effectiveness and safety of 0.12% Chlorhexidine Gluconate have not been established in children under the age of 18.
 
 
 

0.1% Cetylpyridinium Chloride	

• Do not use in children under 6

0.9% NaCl	No contraindications

*\*All mouthrinses are commercially available in the USA, routinely used in clinical settings, and will be used in an on-label manner.*

